### **Methods**

#### **Design Overview**

The proposed study is a multi-site, randomized, clinical trial conducted in a real world setting while collecting implementation data in a Hybrid I design. This study is designed to test the effectiveness of a brief, primary-care based form of CBT-I in a sample of Veterans (N=240) endorsing SI, insomnia, and co-occurring depression or PTSD. Following an initial telephone screening, all patients who agree to participate and who meet all initial inclusion criteria will be asked to participate in the study and to schedule a full baseline assessment. Eligible Veterans will then be randomized to one of two conditions: (1) CBT-I or (2) Sleep Hygiene (SH). All participants will be encouraged to maintain appropriate treatment as usual for their co-occurring condition(s) as recommended by their VA treatment providers. Comprehensive assessments will occur at pre-treatment (baseline), post-treatment (6 weeks), and every 6 weeks until a 6-month follow-up assessment (at 30 weeks).

**Randomization** will occur following informed consent and the subsequent pre-treatment assessment on a 1:1 ratio, stratifying on site, gender and current psychotherapy for depression/PTSD treatment. We will use a stratified block design with block sizes of six. As discussed in the analytic strategy, we will assess for equal distribution of other covariates of interest.

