### Data Analysis and Statistical Considerations

General Considerations. A check of randomness will be conducted for each baseline demographic, meditational, and outcome variable collected using standardized bias estimates. Any estimate greater than .15 will be controlled for statistically in subsequent analyses.

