Power Analysis Considerations. Mixed effect analyses will be used to examine the effects of CBT-I on the developmental trajectories of the primary outcomes of interest; insomnia, depression, PTSD, and SI severity. Here, the power approach for longitudinal mixed effects models put forth by Hedeker, et al. was used. This tests for the statistical power to detect change over time (i.e., slope) using a random effects model (both slope and intercept). For the current proposal, necessary estimates were supplied via pilot results examining unconditional change in SI, depression, PTSD, and insomnia. In all instances, we are interested in the effect of CBT-I on the linear slope (the five time points after the intercept time point) using a two-sided alpha of .05 and .80 power, a 1:1 group ratio, no correlation between intercept and slope, and no correlated residual variance. Higher correlations between intercept and slope and among residual variance both serve to increase power estimates. To help improve power to detect change, two additional data collection time points have been added to this revised proposal. For the outcomes of SI, depression, and insomnia severity, pre-post (6 weeks) standardized effect sizes from the pilot study were all positive and exceeded .40. For power simulations, we tested for linear change from baseline through 6 month follow-up (time points 0, 6, 12, 18, 24 and 30 weeks), testing for the power to detect an effect size of .4 at the 30 week (6 month follow-up) time point. A 20% attrition rate was incorporated into the model, assuming a typical longitudinal attrition pattern with most participants lost early (7% at post-treatment and 5%, 3%, 3%, and 2% at subsequent assessments, respectively). Remaining estimates were supplied via pilot results examining unconditional change in SI, insomnia, depression, and PTSD. For the main outcome of SI, pilot data using the C-SSRS suggests an intercept variance of 10, slope variance of 1.2, and residual variance (error variance) of 24. With these estimates, 240 participants are required to achieve .80 power. Fewer participants are required to achieve .80 power to detect linear change for the remaining outcomes (N = 223 for depression, N = 222, for insomnia, and N= 184 for PTSD) with intercept, slope and residual variances based on pilot data.

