### Data Analysis

[figure not shown]
**Aim 1 Hypotheses (abbreviated):** CBT-I, compared to SH, will be associated with a greater rate of reduction over time in the severity of: **(1a)** insomnia; **(1b)** depression; **(1c)** PTSD; **(1d)** SI.

Mixed effect analyses will be used to test for linear change in each of the above outcomes over time, as well as examining the effects of CBT-I on these trajectories using SAS software (SAS Institute, Inc.). Time will be modeled to reflect baseline status (i.e., time = 0; intercept corresponds to the start point of the trajectory) and time will be a count of weeks from intercept to each follow-up (i.e., 0, 6, 12, 18, 24, and 30 weeks). The effects of CBT-I on the intercept (start point) and on linear change will be examined (effect on intercept expected to be zero due to random assignment). Both intercept and slope will be treated as random effects. Effect sizes (ES) for each outcome, based on work by Feingold, will also be examined. Here, estimates of the means at each time point for each treatment group are derived from the model and used for effect size calculations controlling for the influences of gender, race, ethnicity, and medication use. In addition we recognize that our assumption of linearity may not be met, so we are prepared to examine different trajectories of change to achieve the most parsimonious fit. Specifically, we will examine quadratic change, which suggests rapid change with a plateauing over time, and a piecewise-linear model, which joins together two or more linear trajectories to model non-linearity in the data.]

**Aim 2 Hypotheses (abbreviated):** **(2a)** CBT-I effects on SI at 6 months will be both direct and indirect, mediated by direct intervention effects on *Sleep*, *Depression* and *PTSD*; **(2b and 2c)** 3 month *Depression* and 3 month *PTSD* will be positively related to 6 month SI; and **(2d)** post-intervention *Sleep* will be positively associated with 3 month *Depression*, 3 month *PTSD* and 6 month SI.

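### Aim 1 covariates are picked by a .15 imbalance trigger that chance sets off for about one variable in four, and how they enter the slope model is not stated

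*Combined protocol and SAP*

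**What the plan says.** Under Data Analysis and Statistical Considerations (General Considerations), the plan states: "A check of randomness will be conducted for each baseline demographic, meditational, and outcome variable collected using standardized bias estimates". It continues: "Any estimate greater than .15 will be controlled for statistically in subsequent analyses". The Randomization paragraph of Design Overview points to the same check: "we will assess for equal distribution of other covariates of interest". Randomization itself is stratified by site, gender and current psychotherapy, in blocks of six.

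Aim 1 (Data Analysis) tests the effect of CBT-I on linear change from baseline to week 30 for insomnia, depression, PTSD and SI. The baseline value is the time-0 response, and "Both intercept and slope will be treated as random effects". Race, ethnicity, gender and medication use are named there as controls, but only for the effect-size calculations. The fuller list of demographic, site and baseline clinical covariates given with Figure 2 belongs to the Aim 2 structural equation model.

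The plan does not give the number of variables screened. It does not say whether .15 is an absolute value, or whether a flagged variable enters the Aim 1 model as a main effect or with its interaction with time.

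**The concern.** Under randomisation, an observed baseline difference is chance. A covariate helps the Aim 1 test to the extent that it predicts change over time, and how far the arms happen to differ says nothing about that. The rule can therefore admit irrelevant variables and leave out useful ones. The stratified factors, which the design itself treats as important, are the least likely to be flagged.

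Two things are at stake. The adjusted model for all four outcomes is unknown until the arms have been compared, and with the form of entry unstated, two analysts following the text could fit different models. The baseline data could also sharpen the slope test, and the rule uses them inefficiently.

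**Working it through.** **Inputs from the plan (Power Analysis Considerations).** Design: "using a two-sided alpha of .05 and .80 power, a 1:1 group ratio". Effect: "testing for the power to detect an effect size of .4 at the 30 week (6 month follow-up) time point". Pilot components for SI: "an intercept variance of 10, slope variance of 1.2, and residual variance (error variance) of 24". Dropout of 7, 5, 3, 3 and 2% gives retention of 1, .93, .88, .85, .82 and .80. Result: "With these estimates, 240 participants are required to achieve .80 power".

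**1. The plan's own figure.** Code visits 0 to 5, with V = 10 + 1.2·t·t′ on all pairs of visits and 24 added on the diagonal. The visit variances are 34, 35.2, 38.8, 44.8, 53.2 and 64, so the week-30 SD is 8 and the planning difference is .4 × 8 = 3.2 points. Take c = (−2.5, −1.5, −.5, .5, 1.5, 2.5), divide each V entry by √(r_i·r_j) for retention to get W, and let the effect μ rise linearly from 0 to .4 in units of each visit's SD.

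- c′Wc = 938.3 and c′μ = 11.09
- Total N = 4(1.960 + .842)² × 938.3 / 11.09² ≈ 239.3

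This agrees with 240. The same formula with time in weeks gives 247. No covariate adjustment is needed to reach the figure, so the planned .80 belongs to an unadjusted slope test.

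**2. How often chance triggers the rule.**

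- SE of a standardized difference = √(2/120) = .129
- .15/.129 = 1.162, so P(|d| > .15) = .245
- Read as a signed estimate: .123. At 96 per arm (192 completers): .299

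The number of variables is an assumption. For independent variables:

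| Variables screened | Expected flags | P(at least one) |
|---|---|---|
| 10 | 2.5 | .940 |
| 20 | 4.9 | .996 |

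The clinical scores are likely to be correlated. That leaves the expected counts unchanged but makes the last column only indicative. Stratified factors trigger less often than .245.

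**3. Flagged variables entered as main effects.** With complete data, the slope contrast weights each person's visits by c, which sums to zero. A time-constant covariate therefore drops out exactly. With the planned dropout, simulation at N = 240 with the plan's variance components taken as known (about two flags per trial) gave:

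| | Unadjusted | Rule, main effects |
|---|---|---|
| Level | .052 | .052 |
| Power | .809 | .808 |

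**4. Flagged variables entered with time interactions.** Here person-level slopes are regressed on group and covariates, with 5 or 15 independent continuous covariates. R² is the share of slope variance that they explain together; it is assumed, because the documents give no value.

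| R² | Level under rule | Power under rule | Power, all prespecified |
|---|---|---|---|
| .10 | about .042–.049 | about .80–.81 | about .82–.83 |
| .25 | about .036–.037 | about .82–.83 | about .88–.89 |

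Unadjusted power is about .80 throughout. The prespecified model kept its level at .048 to .055, which is .05 within simulation error. The gap between the last two columns is about 1 to 2 points at R² .10 and 5 to 6 at .25. At an extreme R² of .50 the level under the rule would be about .024–.025 and the gap 10 to 11 points; I do not rest the conclusion on that value.

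The level falls for a simple reason. When a prognostic covariate is imbalanced, the rule removes its contribution. When it is nearly balanced, it contributes little to the estimate's error but stays in the residual variance. The reported standard error is then larger than the real spread of the estimates.

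**The case against.** The rule is prespecified and has a numeric threshold. Each outcome's baseline is in the Aim 1 model whatever happens, as the time-0 response. Site, gender and psychotherapy are balanced by design, and some covariates are fixed for the effect sizes and for Aim 2. All of this stands, and it limits the harm. It does not supply a covariate list or a form of entry for the slope test.

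Three stronger readings are tempting, and the documents do not support them.

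- **That false positives rise.** As a main effect the rule leaves the level alone; with interactions it only lowers it.
- **That the planned power is lost.** The .80 was computed without covariates, and power under the rule stays at about .80 or above in the cases shown. The shortfall is only against a prespecified adjustment that the plan never proposed.
- **That chance imbalance biases the test.** From the plan's variances and complete data, cov(baseline, fitted slope) = −(2.5/17.5) × 24 = −3.43, or −3.43/34 = −.101 per baseline point. A .15 SD imbalance (.15 × √34 = .87 points) therefore shifts the expected week-30 contrast by .101 × .87 × 5 = .44 points, 14% of 3.2. That shift is conditional on the imbalance. It averages to zero over randomisations and is already in the standard error.

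The inert and the conservative result also belong to different readings of the plan. They are alternatives and must not be added together.

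**Conclusion.** The point holds in a limited form. Aim 1 adjustment depends on observed imbalance, which chance alone produces for 24.5% of unstratified variables at 120 per arm (absolute value), and the form of entry is unspecified. As main effects, the flagged variables do practically nothing for the slope test. With time interactions, and covariates that explain 10 to 25% of slope variance, the level is about .036 to .049 and about 1 to 6 power points are forgone against prespecified adjustment. Power does not fall materially below .80.

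The trigger rate follows from the plan's own numbers. The level and power figures rest on assumed R² values and on independent continuous covariates; if no baseline variable predicts change, there is no precision to recover. This is a cheap improvement to an inferior rule and not a threat to the validity of the trial.

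**What to change.** Keep the standardized differences as a descriptive baseline table and remove .15 as a trigger for adjustment. In its place, fix a short Aim 1 covariate list before the arms are compared, to be used whatever the observed balance:

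- the stratification factors: site, gender and current psychotherapy;
- a few baseline variables already collected, chosen for expected prognostic value;
- each entered with its interaction with time, using the same time terms as the treatment effect if a quadratic or piecewise trajectory is adopted.

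For each outcome, keep its own baseline as the time-0 response and do not also enter it as a covariate. The Aim 2 list therefore cannot be copied across unchanged, because it contains the baseline values of the Aim 1 outcomes. State how the new list relates to the controls named for the effect sizes, so that the test and the effect size come from the same model.

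The cost is SAP wording and a few degrees of freedom, with no new data. If the chosen variables do not predict change, there is little or no gain, which is a reason to keep the list short.

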### Data Analysis

[figure not shown]
**Aim 1 Hypotheses (abbreviated):** CBT-I, compared to SH, will be associated with a greater rate of reduction over time in the severity of: **(1a)** insomnia; **(1b)** depression; **(1c)** PTSD; **(1d)** SI.

Mixed effect analyses will be used to test for linear change in each of the above outcomes over time, as well as examining the effects of CBT-I on these trajectories using SAS software (SAS Institute, Inc.). Time will be modeled to reflect baseline status (i.e., time = 0; intercept corresponds to the start point of the trajectory) and time will be a count of weeks from intercept to each follow-up (i.e., 0, 6, 12, 18, 24, and 30 weeks). The effects of CBT-I on the intercept (start point) and on linear change will be examined (effect on intercept expected to be zero due to random assignment). Both intercept and slope will be treated as random effects. Effect sizes (ES) for each outcome, based on work by Feingold, will also be examined. Here, estimates of the means at each time point for each treatment group are derived from the model and used for effect size calculations controlling for the influences of gender, race, ethnicity, and medication use. In addition we recognize that our assumption of linearity may not be met, so we are prepared to examine different trajectories of change to achieve the most parsimonious fit. Specifically, we will examine quadratic change, which suggests rapid change with a plateauing over time, and a piecewise-linear model, which joins together two or more linear trajectories to model non-linearity in the data.]

**Aim 2 Hypotheses (abbreviated):** **(2a)** CBT-I effects on SI at 6 months will be both direct and indirect, mediated by direct intervention effects on *Sleep*, *Depression* and *PTSD*; **(2b and 2c)** 3 month *Depression* and 3 month *PTSD* will be positively related to 6 month SI; and **(2d)** post-intervention *Sleep* will be positively associated with 3 month *Depression*, 3 month *PTSD* and 6 month SI.

Structural equation modeling (SEM) will be used to test these mediational hypotheses. The structural model to be tested is presented in **Figure 2**, illustrating key mechanisms/processes for how CBT-I influences suicide risk in Veterans. Modeling the processes underlying interventions, that is, addressing questions of “how” do interventions work, is a key benefit of SEM techniques. As noted in the model, SI at 6 month follow-up is the key outcome of interest (SI Severity as assessed by the SSI total score). We hypothesize that intervention effects on 6 month SI are not exclusively direct, but that CBT-I effects on *Sleep* and *Depression* and *PTSD* mediate the intervention effects on SI. In the model, SI will be measured by 6 month SSI. *Depression* will be measured using two indicators from the 3 month follow up assessment, the PHQ-9 (omitting the SI and the sleep items) and the Beck Hopelessness Scale. *PTSD* will be measured using a single indicator from the 3 month follow-up assessment, the PTSD-Checklist score (omitting the insomnia item) *Sleep* will be measured using three manifest indicators from the immediate post assessment point, the total ISI score and two sleep diary indicators (Percent Sleep Efficiency and Total Sleep Time). *Treatment* status will be measured with a dichotomous CBT-I group variable. The single indicator latent variables (*Treatment*, *PTSD*, and *SI*) will be modeled with the assumption that it is completely reliable (i.e., residual variance = 0). As one form of sensitivity, we will adjust *PTSD* and *SI* based on internal reliability estimates.

**Figure 2. Proposed structural model to be tested**

NOTE: ↙ denotes residual variance unexplained in the model. Residual covariance among Depression and PTSD as well as demographic covariates and medication use have been omitted for presentation clarity (see text). FU = Follow-Up; HS = Beck Hopelessness Scale; ISI = Insomnia Severity Index; SE% = Percent Sleep Efficiency; PHQ9 = Patient Health Questionnaire; SSI = Scale for Suicidal Ideation; TST = Total Sleep Time.

Key demographic variables (gender, age, minority status), site, (Rochester, Syracuse vs. Buffalo), and baseline values of clinical variables (SI, insomnia, nightmares, depression, PTSD, concomitant medications) will be statistically controlled for in the model. The Mplus statistical package will be used to test the SEM.

To provide a metric for each latent construct and to identify the model, the first construct loading for each latent variable will be set at 1.0. Following Anderson and Gerbing, a two-step approach examining the model will be undertaken. First, using confirmatory factor analytic techniques, a test of the proposed measurement model will be conducted and any needed modifications to this model will be undertaken prior to examining the fit of the full model. The second step in this methodology involves an examination of the structural portion of the model. As shown, the model suggests that CBT-I effects on SI Severity are both direct and indirect, mediated by effects on Sleep, Depression and PTSD. In the model, baseline severity of Sleep, Depression, PTSD and SI will be statistically controlled for, aiding precision in detecting treatment effects. Fit of the model will be assessed using the associated chi-square statistic, as well as the more approximate fit indices of the root mean square error of approximation (RMSEA), the comparative fit index (CFI), and the standardized root mean square residual (SRMR). Hu and Bentler empirically examined various cutoffs for many of these approximate fit indices and their data suggest that to minimize Type I and Type II errors under various conditions, one should use a combination of cutoffs for fit assessment. They recommend that adequate fitting models have  $CFI > .95$ ,  $RMSEA < .06$ , and  $SRMR < .08$ ; such recommendations will be adopted here.

CBT-I indirect effects on 6 month SI severity (i.e., via Sleep, Depression, and PTSD) will be tested using the bias-corrected confidence limits. Each of the three indirect effects (9 total) will be assessed for significance as will the overall total effect. Significance will be assessed by whether or not the 95% confidence limits contain zero. The bias-corrected approach takes non-normality of the multiplicative distribution into account, resulting in asymmetric confidence limits and has been shown to provide the most accurate confidence limits and greatest statistical power when compared with other existing approaches for detecting mediation.

**Exploratory Aims:** As described under *Therapist Fidelity* in the *Measures* section, we will rate both adherence and competence to the CBT-I intervention. Interrater reliability will be assessed using the kappa statistic and intraclass correlation approach. Once established  $> .8$  agreement), we will calculate and report on the therapist fidelity to treatment (from adherence measures) and competence in delivering the intervention (from competence measures). Exit and therapist interview data will be assessed for thematic content by using a conventional content analysis approach to avoid imposing preconceived themes/categories on the data. Inductive coding will be used by two research staff trained by [name] to listen to the interviews and develop preliminary sets of codes. The two research staff will independently rate one interview at a time, meet to discuss their coding process for that interview, and reach consensus on codes created and applied until

agreement on code definitions can be used consistently. All analytic decisions will be documented. Remaining interviews will be analyzed independently, but regular meetings will be held to discuss the evolving analysis and how similar codes cluster together. Once complete, discussion of the codes within and across categories of data and interpretation of themes across categories will occur. Themes, categories, and specific codes that emerge can be used to inform any subsequent implementation efforts.

If treatment attitudes instruments are normally distributed, ANCOVA will be used to test for significant treatment effects from baseline to post-treatment among those participants not engaged in psychotherapy at baseline, otherwise non-parametric tests will be applied (with covariates statistically controlled).

Missing Data. Mixed effects models and SEM incorporating full-information maximum likelihood make efficient use of all available data; we will also conduct analyses using multiple imputation of missing data as a form of sensitivity analysis. Multiple imputation uses a regression based approach to impute values for data that are missing, providing that data meets the missing at random criteria. To improve estimates, the procedures put forth by Allison regarding intervention studies will be followed. Here, each treatment condition is imputed separately and resulting datasets are merged. Following Rubin, ten imputations will be performed and each resulting datasets will be analyzed as above. The results obtained will be combined following the techniques employed by Rubin. Multiple imputation has consistently demonstrated less biased parameter estimates than most other traditional approaches to the handling of missing data. If missingness appears biased by treatment condition, a pattern-mixture approach to missing data will be assessed. Here, different patterns of missingness are identified and participants are placed into groups based on their missingness pattern. Dummy variables representing group membership are entered into the mixed effect and SEM analyses; intervention by group membership interaction terms are assessed to examine for differential effects on outcomes dependent on missing data patterns.

The SEM to be tested will make use of the full-information maximum likelihood estimation method, which uses estimates throughout the model to provide more accurate estimates where data is missing. Again, this approach provides more realistic parameter estimates than other missing data techniques when data is missing at random or missing completely at random.

Type 1 Error Protection. To help control for Type 1 error, the Benjamini-Hochberg (BH) method will be used to adjust for the multiple comparisons proposed in the current study. The BH method adjusts for multiple comparisons by controlling false discovery rate instead of family-wise error rate. It is less conservative than the more traditional Bonferonni methods, yet still provides adequate protection against Type 1 error. Since its inception, there has been growing evidence suggesting that the false discovery rate based BH method is the optimal solution to the multiple comparison problem in most practical situations.

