Fourth, with HSRD pilot award support (HX001473) we conducted a small randomized trial of our 4-session primary care version of CBT-I compared to treatment-as-usual in primary care. A total of 50 Veterans with insomnia, recent SI and either MDD and/or PTSD completed the study. The effect sizes (conservatively adjusted for sample size) were very large for insomnia ( $g = 1.79$ ) and depression ( $g = 1.19$ ;  $g = 1.13$  with sleep item removed) and modest for SI Intensity ( $g = 0.44$ ). While it is modest, the effect size for SI is in line with effects observed in a study of dialectical behavior therapy for women Veterans with borderline personality disorder and similar or larger than effects achieved by depression psychotherapies.

Fifth, for the HSRD pilot we developed reliable therapist fidelity measures for Adherence to the treatment manual for all 4 CBT-I sessions and Competence in delivery of the CBT-I using gold standard observational methods.

Finally, the HSRD pilot provides recruitment & retention feasibility. We enrolled 54 participants over 8 months (~7 per month) and retained 50 (7.4% attrition rate). This was achieved using two primary care clinics at the Canandaigua VA Medical Center (one at the VAMC and one at its Rochester Outpatient Clinic). This was also accomplished at the same time that our study team was successfully recruiting primary care patients with depression for another study. This demonstrates our ability to recruit participants at these sites. In the current application, we propose to add primary care clinics at two additional VAMC's (Syracuse and Buffalo), which will significantly enhance recruitment capacity. Although these data are for a study that did not have longer term follow-up assessments, the high retention rate is a promising indicator for the proposed study.

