### **Specific Aims**

**Aim 1: To test the direct effects of a brief CBT-I intervention, compared to SH, on the trajectories of severity of insomnia, depression, PTSD and SI through 6 month follow-up.**

**Hypothesis 1a:** CBT-I, compared to SH, will be associated with a greater rate of reduction in severity of insomnia over time.

**Hypothesis 1b:** CBT-I, compared to SH, will be associated with a greater rate of reduction in depression severity over time.

**Hypothesis 1c:** CBT-I, compared to SH, will be associated with a greater rate of reduction in PTSD severity over time.

**Hypothesis 1d:** CBT-I, compared to SH, will be associated with a greater rate of reduction in SI severity over time.

**Aim 2: Utilize structured equation modeling to determine if (and how) effects of CBT-I on SI are mediated by sleep, by depression and by PTSD.**

**Hypothesis 2a:** CBT-I effects on SI at 6 months will be both direct and indirect, mediated by direct intervention effects on sleep, depression, and PTSD.

**Hypothesis 2b:** Depression at 3 months will be positively related to SI at 6 months.

**Hypothesis 2c:** PTSD at 3 months will be positively related to SI at 6 months.

**Hypothesis 2d:** Post-intervention sleep will be positively associated with 3 month depression, 3 month PTSD, and 6 month SI.

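### The Aim 2 mediation model controls symptoms only at baseline, so symptoms that change together afterwards can be reported as serial mediation, and no planned check would detect it

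*Combined protocol and SAP*

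**What the plan says.** Under Data Analysis (Aim 2), each construct in the structural model is taken from one visit. Sleep "will be measured using three manifest indicators from the immediate post assessment point", which is week 6. Depression "will be measured using two indicators from the 3 month follow up assessment" and PTSD "will be measured using a single indicator from the 3 month follow-up assessment"; the compensation schedule under Procedures places that visit at week 18. SI is the SSI at the 6-month follow-up, week 30.

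The text after Figure 2 lists the adjustment variables: demographics, site, and baseline values of the clinical variables. It adds: "In the model, baseline severity of Sleep, Depression, PTSD and SI will be statistically controlled for, aiding precision in detecting treatment effects". The only residual covariance named is the one between Depression and PTSD.

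An indirect effect is declared when its 95% bias-corrected limits exclude zero. The planned sensitivity work covers the reliability of PTSD and SI (Data Analysis) and missing data (Missing Data). Multiplicity is handled by Benjamini-Hochberg (Type 1 Error Protection).

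Table 1 schedules the PHQ-9, BHS, PCL-5 and SSI at every visit from pre-treatment to week 30. The interim values therefore exist but do not enter the model as described.

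**The concern.** Treatment arm is randomized; the mediators are not. The staggered visits are meant to supply a time order of sleep, then depression and PTSD, then SI. Time order alone does not remove confounding by symptom levels that have already moved by the earlier visit.

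The plan expects such movement. Preliminary Data reports pilot effects that "were very large for insomnia" (g = 1.79), with 1.19 for depression and 0.44 for SI Intensity. Power Analysis Considerations describes the pre-post (6-week) effects on SI, depression and insomnia as all positive and above .40.

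If week-6 depression is left out, week-6 sleep partly stands in for it when predicting week-18 depression. If week-18 SI is left out, week-18 depression partly stands in for it when predicting week-30 SI. A trial in which symptoms improved together and stayed improved could then look like one in which sleep drove later depression and depression drove later SI. Hypothesis 2a, the mediation claim, depends on telling these apart.

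**Working it through.** **The plan's own figure.** The only Aim 2 power statement concerns global fit: above .98, with 136 degrees of freedom, RMSEA .05 against .08. With noncentrality (N − 1) × df × RMSEA² and N = 192 completers, the values are 191 × 136 × .0025 = 64.9 and 191 × 136 × .0064 = 166.2. At alpha .05 the power is .984, so the figure reproduces. It says nothing about the indirect effects.

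**Inputs.** From the documents: 192 completers, 1:1 allocation, visits every 6 weeks, and the modelled visits 0, 6, 18 and 30. Assumed, because the documents give no values: arm effects at week 6 of 1.0 SD (sleep), 0.6 SD (depression) and 0.3 SD (SI), within-visit correlation ρ of .3 to .5, equal autoregression for each symptom, and no effect of one symptom on another at any lag.

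**Why the path is biased.** Let φ₁₂ be the autoregression over 12 weeks. Given arm and baseline, the slope of week-6 depression on week-6 sleep is ρ. With week-6 depression omitted, the expected Sleep(6) → Depression(18) coefficient is φ₁₂ × ρ instead of zero.

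Example with .6 per 6-week visit and ρ = .5:
- φ₁₂ = .6² = .36, so the spurious coefficient is .36 × .5 = .18.
- Residual variance of week-6 sleep: 1 − .36 = .64 (SD .8).
- Variance of week-18 depression given baseline: 1 − .6⁶ = .953. Less .18² × .64 = .021, this is .932 (SD .966).
- Standard error: .966 / (.8 × √186) = .089, so the expected z is .18 / .089 = 2.0. A false positive follows in about half of trials.

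Simulation gave 54% for this path in that setting.

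**False serial path (arm → sleep → depression → SI), planned adjustment.** Path regressions were used, and the path counted as present when every step was significant at .05.

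| Assumed autoregression | ρ = .3 | ρ = .4 | ρ = .5 |
|---|---|---|---|
| .6 per 6-week visit (φ₁₂ = .36) | 6% | 14% | 33% |
| .8 per 6-week visit (φ₁₂ = .64) | 28% | 62% | 83% |
| .6 across each 12-week gap | 33% | 66% | 91% |

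Repeat runs of the first row gave 6–7%, 14–17% and 32–35%. Adding week-6 depression and SI at weeks 6 and 18 brought the serial rate below 1% and each single path to about 5%.

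**Second check, different generator.** This one included PTSD and 30% noise variance, with correlation .8 between modelled visits and assumed arm effects of 0.8 on sleep, 0.4 on depression and PTSD, and 0 on SI. The false total indirect effect was 3.5% with no shared post-baseline change. It was 35%, 76% and 90% with 20%, 40% and 60% shared variance, and about 4% once interim values were added. With correlation .5 and 40% shared, it was 27%.

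**What the interim adjustment costs.** When the true chain acts after the interim visits, detection at path sizes .15, .25 and .35 was 36%, 90% and 99.6% with interim values, against 28%, 84% and 99.9% as planned. When sleep lowers depression within the 6-week treatment window, the planned model detected the chain in 57–98% of trials and the lagged model in under 1%.

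**The case against.** A reader might infer that co-moving symptoms are bound to be reported as mediation. The documents do not support that. Co-movement already captured by the baseline scores did no harm (3.5%). A false indirect effect also needs an arm effect on the mediator: with no arm difference in sleep (N = 240, 40% shared), the three sleep-led paths were flagged in only 1–2.5% of runs, although arm → depression → SI still was in 50%. With .4 per visit and ρ = .3 the serial rate is about 1%.

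The tabled rates come from observed-variable regressions without PTSD, measurement error or Benjamini-Hochberg adjustment. At .6 per visit and ρ = .4, reliability of .8 cut the serial rate from 17.5% to 6%. Figure 2 is not shown, so the paths were read from the text and the figure note.

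It is also tempting to say that all of H2a–H2d are undermined. H2b–H2d are worded as associations; H2d reads "Post-intervention sleep will be positively associated with 3 month depression, 3 month PTSD, and 6 month SI". Shared change satisfies that wording. The concern reaches H2a and any causal reading of the other paths.

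The strongest objection is to replacing the planned model. CBT-I is delivered over 6 weeks, and depression relieved by better sleep during those weeks is mediation in the plan's own conceptual model. Conditioning on week-6 depression removes it. That objection stands, and it rules out substitution.

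The existing safeguards are real: ordered visits, a randomized arm, baseline control, and removal of overlapping PHQ-9 and PCL items. They remove shared content and stable severity, but not shared change after baseline. Benjamini-Hochberg addresses multiplicity, not a biased path.

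**Conclusion.** The concern holds in a conditional form. With symptom control at baseline only, sleep, depression and SI that change together after baseline can be reported as serial mediation, and nothing planned would detect it. Depending on the persistence assumed, the false serial-path rate runs from about 6–33% to 33–91% over within-visit correlations of .3 to .5. Neither the correlation nor the autoregression is in the documents, so no single rate can be assigned to this trial. Neither model identifies mediation without assumptions: the planned one can mistake shared change for a chain, and the lagged one misses a chain completed by week 6. Aim 1 does not depend on this model. This is a cheap improvement to the plan.

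**What to change.** Keep the planned model and prespecify a lagged one beside it:
- Add week-6 Depression (PHQ-9 without the SI and sleep items, and BHS) and week-6 PCL-5 as predictors of their week-18 values.
- Add week-6 and week-18 SSI as predictors of week-30 SSI.
- Allow residual covariances within each visit.
- Claim time-ordered mediation (sleep, then depression/PTSD, then SI) only if the indirect effect also holds in the lagged model. If it appears only in the baseline-adjusted model, report it as compatible with either mediation during treatment or shared change.
- State the assumption of no unmeasured mediator–outcome confounding.
- State in advance that a null lagged result is not evidence against mediation, because that model has almost no power for mediation already completed by week 6.

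The cost is SAP wording and extra paths in Mplus. No new data are needed.
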